1 BACKGROUND

Cystic Fibrosis

Cystic fibrosis is a hereditary condition that for most leads to a significantly shortened lifespan and impaired quality of life. The CF research community has strived for new interventions to improve lung health with dramatic improvements in patient survival over the last 20 years. Beginning with enhanced lung clearance techniques, Pulmozyme, and new antibiotics providers saw a jump in the life expectancy of CF patients between 1995 and 2010. (Keogh, Szczesniak, Taylor-Robinson, & Bilton, 2018) Previous work has resulted in a very good understanding of the genetics behind the mutations that lead to the CFTR protein alterations and the varying phenotypes of the disease. The CF foundation is now projecting a doubling of the life expectancy of CF patients in the next 10 years ("Cystic Fibrosis Trust Cystic fibrosis registry report 2017. , "

2017;"Resources/Patient-Registry/Understanding-Changes-in-Life-Expectancy., "2016; Stephenson et al., 2017; Sykes et al., 2016; "WHO Guidelines Approved by the Guidelines Review Committee," 2010) much of which is related to the CFTR modulator therapies current and under development. More successes over the next decade will likely move cystic fibrosis

from a disease that kills young adults to a disease that people live with into old age. Aging gracefully means clinicians must look at the totality of care for these patients and specifically at quality of life factors such as exercise, diet, and sleep patterns and the interplay these factors have on lung health, glycemic control, bone health and general wellbeing with a goal to improve all aspects of care so that the patient living with CF has the best possible quality of life.

People with chronic illness often end up with an imbalance of the core components of a balanced healthy lifestyle including adequate sleep, regular exercise and a balanced diet. Once this imbalance is present there is a much higher chance that these factors will contribute themselves to additional medical complications as well as decreased quality of life and increased mental health issues.

Physical activity is recognized by the World Health Organization as a crucial component to maintaining health and preventing disease ("WHO Guidelines Approved by the Guidelines Review Committee," 2010). Several studies have shown that physical activity is independently related to aerobic capacity in cystic fibrosis (CF) (Hebestreit et al., 2006).

The CF community has also recognized the value of regular exercise and studies have demonstrated that regular physical activity can positively impact lung function (Kriemler et al., 2013), improve general wellbeing, exercise tolerance and bone health in patients with CF (Tejero Garcia et al., 2011).

Small studies in adults with CF suggest that those with poorer lung function suffer with exacerbations more frequently than those with better lung function (Savi et al., 2015). Short-term (6-8 weeks) inpatient and outpatient rehab programs for CF patients have shown improved overall lung function and exercise capacity (Gruber, Orenstein, Braumann, Paul, & Huls, 2011; Santana Sosa et al., 2012). In addition, one small 12-month study in children suffering from CF demonstrated that exercise reduces CF exacerbation frequency (Urquhart et al., 2012). While other small and short-duration studies have demonstrated similar improvements, it is not clear that a change in one's exercise and conditioning routine can alter the frequency of exacerbations seen in adults with CF.

Decades of research has demonstrated that chronically deficient sleep (time or quality) results in higher risk for poor health: everything from mental health issues to accidents to excess risk for obesity and cardiovascular disease and even premature death. ("Centers for Disease Control and Prevention. Insufficient sleep is a public health problem., "; Luyster, Strollo, Zee, & Walsh, 2012; Van Dongen, Maislin, Mullington, & Dinges, 2003; "WHO-Europe Bonn Germany, January 22-24, 2004 (Role of Sleep in health)," 2004) There are limited studies of sleep and disorders of sleep in CF. Generally, the findings point to poorer quality (decreased deep sleep, increased awakenings, increased daytime sleepiness) (Amin, Bean, Burklow, & Jeffries, 2005; Dancey, Tullis, Heslegrave, Thornley, & Hanly, 2002; Milross et al., 2002; Vandeleur et al., 2017). The reason for this poor sleep is only partly explained by CF exacerbation or declining lung function. Defective expression of CFTR (expand CFTR) gene in

certain areas of brain (specifically the retina and anterior hypothalamus) could contribute to both changes in the timing of sleep and the quality of sleep (Jensen et al., 2017). The role of sleep alterations in glucose metabolism has been studied (Gonzalez-Ortiz, Martinez-Abundis, Balcazar-Munoz, & Pascoe-Gonzalez, 2000; Punjabi et al., 2002), but no clinical study of CF Related Diabetes and sleep patterns or exercise patterns has been completed (Hardin, Leblanc, Marshall, & Seilheimer, 2001).

The newest personal fitness monitors allow for both short term and long-term trending in activity and sleep and are both affordable and easy to operate. Data generated by this technology afford the possibility of better understanding one's personal state of general wellness from how much activity to the level of intensity to the quality and quantity of sleep one is getting. The role of an activity monitor in improving activity and fitness has been studied and may have the most impact

on those with lowest activity levels in some populations (Beattie et al., 2017; Schrager et al., 2017). Regarding sleep tracking, the validity of sleep tracking programs has also been assessed and total sleep time and sleep quality can be measured with fair accuracy (de Zambotti, Baker, & Colrain, 2015; Meltzer, Hiruma, Avis, Montgomery-Downs, & Valentin, 2015).

Fitness trackers could be helpful for those with CF through evaluating general trends in activity level, intensity of activity and sleep quality and timing (Jankelowitz et al., 2005). Further, integration of data from wearable health tracking with objective biologic/medical data would allow analysis of trends between these core components of a healthy lifestyle and medical outcomes.

The CF community has been collecting biologic/medical data on patients now for over 30 years through the CF Foundation Patient Registry (CFFPR). This provides individual as well as center specific trends through tracking weight/BMI, lung function, frequency of exacerbations as well lab and test results such as glycemic control and bone density results. This data has assisted CF centers in improvements in care delivery (Warwick, 2001) through quality improvement (Johnson,

Butler, Konstan, Morgan, & Wohl, 2003) and best practice sharing between centers (Schechter, Fink, Homa, & Goss, 2014). In 2017 all centers have now risen to near real-time reporting of lung function, exacerbation rates, weight and diabetes control trends for patients to encourage conversations and real behavior change around medical adherence.

The objective of this pilot study is to demonstrate the feasibility of integrating the personal health tracker data with the medical data stored in CFFPR to facilitate larger multicenter interventional studies to continue improving care in this deserving population.

Methods

Potential subjects will be identified during regular team meetings held by a dedicated care team for CF patients that includes members of the study staff. Patients who are identified as potential participants will be contacted by a trained member of the study team to discuss participation. The study team will work with patients to arrange for signing of an informed consent form at their next scheduled clinic appointment.

All subjects will be consented to participate in this observational study for a minimum 3 months to accommodate their clinic schedule. There will be a minimum of 2 clinical visits after enrollment (clinical visit 1 at set up and 2-5 months follow up) as well as any sick visits. This visit schedule was selected to coincide with current care schedules.

At the initial visit all consented subjects will be provided a Fitbit Inspire HR and shown the proper use and care of the tracker. The research coordinator will confirm the subject's ability to upload data from the device to their study Fitbit account (deidentified) under direct observation. The subjects will also receive instruction in how to document their activity and sleep in the diary app associated with their Fitbit. (The subjects will have access to instructional videos and help desk

through the Fitbit resource center as well). The research coordinator will monitor the study specific FitaBase for the duration of the study (once a week for 3 months) and contact the patient via their preferred method of contact with encouragement to consistently upload data if needed.

During the initial visit and any follow up clinic visits subjects will complete a general quality of life in CF survey-CF QOL and a sleep quality index-Pittsburgh Sleep Quality Index (PQSI) through Redcap to assist in a comprehensive integration of data.

This study will quantify the activity and sleep patterns of the CF patients through use of the provided fitness monitor (Fitbit- Inspire HR) that measures heart rate, activity level (number of steps, intensity of exercise (moderate to intense based on HR vs movement on GPS-Fitbit analytics), sleep time and quality of sleep over 3 months. To provide the most accurate data from the device subjects will need to sync their device at least every 5 days to keep the 5-minute and 1-minute data for the prior days of use. The process of synchronization/downloading is nearly effortless for those with a smart phone or computer as every time the device is near these devices it should download the data collected. In addition, the Fitbit app and website has additional programs including a diary where subjects can document their exercise, activity and even sleep habits. Whenever possible the subject will document their activity through this app to provide validation of the data collected by the sensors.

The FitaBase has preset analysis functions to allow for data report at daily, weekly, monthly intervals. The is a deidentified database and subjects will be given assigned subject codes for this database to prevent sharing of identifiable information. To further secure patient privacy, all subjects will have a study email account set up to tie to the trackers during the study.

Quality control for Fitbit data will include confirming Fitbit uploads weekly (remote access) and comparison of this data against the patient activity/sleep diary entry for accuracy at the time of the phone conversation at 1 week and 1 month and all clinical visits (sick visit/s, Month 3).

At each CF clinical visit (initial visit, routine scheduled checkup, and any sick visits/hospitalization) the research team will check in with the subjects and confirm there are no issues or concerns with the device and/or address study compliance issues.

If a Fitbit stops working, the Fitbit program will be notified by the research coordinator and a new device sent to the research site to be dispensed by the research coordinator to the subject (via mail or in person) after confirming it is tied to the subject number's appropriate account in FitaBase. Additional devices will be available to the research site to dispense in the event of a lost device (not supported by the Fitbit care program).

Clinical care visits and hospitalizations during the trial period of three months will be entered into the CFFPR national database (standard practice). Data of specific interest include: lung function (FEV1), BMI, and CF exacerbation rates. The exacerbation will be defined by the treating CF provider (generally this is reported as part of each visit (key features of a CF exacerbation include all the following but does not require any more than 3 of the following: Weight loss (>2 lbs.),

increased cough/increased sputum production, disturbed sleep due to coughing, increased fatigue/inability to do daily activities due to breathing problems/fatigue, fevers, fall in FEV1 by 5% or more)).

Any technical questions from the patient regarding the data collected by the fitness tracker will be answered by the research coordinator.

2 HYPOTHESIS AND OBJECTIVES

This pilot, single center, correlational study will provide proof of concept for integrating existing medical data from CFFPR with long term monitoring of patterns in sleep and activity available through individual fitness trackers (i.e. Fitbit).

The data collected for each subject from the personal fitness monitors will be trended with daily, weekly and monthly averages over 3 months (activity level, time and intensity of exercise, sleep total time and quality

(percentage deep sleep). This information will be coupled with the CFFPR data health parameters as reported with every clinic visit and any hospitalizations for each subject.

2.1 Aims

AIM 1: Demonstrate that participants will consistently use and upload data from the fitness tracker as measured by use of at least 20 hours per day and uploading of at least 75% of activity.

AIM 2: Develop integration tool for the data from the Fitbit with data from CFFPR.

AIM 3: Analyze the data trends from the Fitbit for activity and sleep with health trends from the CFFPR (FEV1, BMI, exacerbation rates).

3 STUDY DESIGN

3.1 General Description

The study center has identified 147 adult patients ranging from 18 to 69 years of age with CF. For this feasibility study a total of 21 patients will be enrolled and while we will not assign patients to cohorts or limit enrollment based on lung function at the end of the study, we will stratify enrolled patients to explore trends. The cohorts will be constructed ad hoc to facilitate an accurate and clinically meaningful analysis. This will allow for trend analysis to see if more advanced disease is a factor in adherence to use of the Fitbit and an exercise regimen.

The study will be carried out by a dedicated research group consisting of seven full time research coordinators, a research assistant, and a part-time systems specialist within the PI's Division that has conducted numerous trials and continues to support a robust and successful CF research program. The study will be assigned at minimum two research coordinators to provide every eligible patient the opportunity to participate. The study research coordinator group has previous experience with fitness tracker software and management of deidentified database related to a fitness tracker used in a large multicenter clinical trial.

Number of Subjects

Up to 21 patients may be consented into this trial. Twenty-one patients are needed to meet the aims of this trial.

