3.1.1 Primary Endpoint(s)

For Aim 1 and Aim 2 we will report descriptive statistics, such as mean, median and standard deviation, for the number of days of use, days of use over 20 hours and average hours of use per day (total hours of use/total days of use) in the study. Secondary Endpoint(s)

For Aim 3. We will conduct explorative data analysis to get preliminary information for designing a full-scale prospective study. First, we will report summary statistics, such as mean, median, standard deviation and quartile range, for continuous measurement and percentage for binary measurement, of heart rate, activity levels, sleep time and quality of sleep for every month and summary statistics for FEV1, BMI and CF exacerbation at enrollment and follow-up visit and differences between enrollment and follow-up visit. To identify what information of heart rate, activity levels, sleep time and quality of sleep is potentially associated with the differences between enrollment and follow-up visit in FEV1 and BMI and CF exacerbation, we will use Pearson correlations for FEV1 and BMI and comparing means or medians of the wearable metrics between the subgroups with and without CF exacerbation in 3 months. We will also consider mean or median values of the wearable metrics measured last 3-/2-/1-month prior to the follow-up to determine the extent to how latest metrics are associated with clinical outcomes.

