5.2 Study Withdrawal Procedures

5.2.1 Duration of Therapy: A patient may remain in the study up to 3-months.

5.2.2 Patient-Initiated Withdrawal: A patient may decide to withdraw from the study at any time.

5.2.3 Investigator-Initiated Withdrawal: The Investigator will withdraw a patient whenever continued participation is no longer in the patient's best interests. Reasons for withdrawing a patient include, but are not limited to, disease progression, the occurrence of an adverse event or a concurrent illness, a patient's request to end participation, a patient's noncompliance or simply significant uncertainty on the part of the Investigator that continued participation is prudent.

5.2.4 Withdrawal Documentation Procedure: The reason for study withdrawal and the date the patient was removed from the study must be documented in OnCore.

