6 TREATMENT PLAN

6.1 Standard of Care Procedures

6.2 Follow-Up Period

Patients will be followed for 90 days after enrollment or until death, whichever occurs first.

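### Disease severity and Fitbit adherence are to be explored in cohorts built ad hoc from 21 patients, with no cut-points; a pre-named correlation with continuous baseline FEV1 is a cheap improvement

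*Combined protocol and SAP*

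**What the plan says.** Section 3.1 states: "we will not assign patients to cohorts or limit enrollment based on lung function at the end of the study, we will stratify enrolled patients". The purpose of that step is exploratory. The section then adds "The cohorts will be constructed ad hoc to facilitate an accurate and clinically meaningful analysis", and gives the question as "to see if more advanced disease is a factor in adherence to use of the Fitbit and an exercise regimen". Lung function is the natural reading of the stratifying variable, but the sentence does not commit to it, and it is unclear which clause the reference to the end of the study belongs to.

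No other section fills the gap. Section 3.1.1 lists the use measures, among them "days of use over 20 hours and average hours of use per day", but does not relate them to severity; its Pearson correlations concern wearable metrics against change in FEV1 and BMI. Section 9.5 says only who provides statistical support. No exercise regimen is defined anywhere, so only device use can be scored as adherence.

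Baseline FEV1 is available: section 3.1.1 promises "summary statistics for FEV1, BMI and CF exacerbation at enrollment and follow-up visit", and the Study Calendar has lung function at enrollment.

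**The concern.** With 21 patients, where a cut falls can decide whether a trend appears. The coordinator checks uploads weekly (section 1, Methods), so by study end the adherence pattern is known to the team. Cohorts formed then, without a rule, may or may not be independent of that pattern, and a reader of the results could not tell which.

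This is the only planned look at severity and adherence. Section 3.1.1 says that the exploratory Aim 3 results are to inform a full-scale study, and a severity signal from this pilot could be used in the same way. Cuts fixed in advance would remove the problem but discard some information about FEV1.

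**Working it through.** **Inputs from the documents.** n = 21 (3.1); two-sided 95% intervals, with widths 0.856 and 0.193 at r = 0.1 and 0.9 (9.2). The documents give no correlation between severity and adherence, so 0.3, 0.5 and 0.6 are assumptions.

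**The plan's own figure.** The width of tanh(atanh(r) ± 1.96/√(n − 3)) with n − 3 = 18 is 0.856 at r = 0.1 and 0.193 at r = 0.9. Both stated values reproduce.

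**Cuts chosen after adherence is seen (illustration).** Simulated bivariate normal data, no true relation, 200,000 datasets, share with nominal p < 0.05:

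| Analysis | Share |
|---|---|
| Spearman, continuous FEV1 | 5.1% |
| Best of three cuts (7/14, 10/11, 14/7) | 11.7% |
| Best of all cuts with 5 or more per group | 22.5% |

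**Cuts fixed in advance, roughly linear relation.** Power at two-sided 5%, 100,000 datasets per setting:

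| Assumed correlation | Spearman | Tertile trend (7/7/7) | Median split (10/11) |
|---|---|---|---|
| 0.3 | 23.6% | 21.3% | 17.9% |
| 0.5 | 59.7% | 54.6% | 44.3% |
| 0.6 | 79.4% | 74.3% | 62.4% |

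Spearman leads the tertile trend by 2.3, 5.1 and 5.1 points, and the median split by 5.7, 15.4 and 17.0 points. Large-sample information agrees. Relative to a linear analysis of a normal variable, Spearman keeps 9/π² = 0.912, a tertile trend 0.793 and a median split 2/π = 0.637. Relative to Spearman, tertiles keep 0.793/0.912 = 0.87 (like 18 of 21 patients) and a median split 0.637/0.912 = 0.70 (like 15 of 21).

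**Threshold relation.** With an assumed step of 1.2 SD at the lowest third, power is about 43% for Spearman, 43% for the tertile trend, 49 to 50% for a correctly placed 7/14 cut and 39 to 40% for a median split.

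**Precision.** For an observed Spearman correlation of 0.3: tanh(0.3095 ± 1.96 × √((1 + 0.3²/2)/18)) = tanh(0.3095 ± 0.4723), that is −0.16 to 0.65.

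**Why the denominator and scoring need stating.** Assume no true relation, personal adherence drawn from Beta(7,3), 90 days and a uniform withdrawal day. With 1, 2 or 3 withdrawals in the lowest FEV1 third, the mean Spearman correlation is 0.08, 0.15 or 0.22 on a fixed 90-day denominator, and 0.00 throughout on days in the study. With 3 patients in that third each having 20%, 30% or 50% of days unsynced, it is 0.16, 0.22 or 0.27 if those days count as not met, and 0.00 if they are treated as missing. By construction this shows only what happens when withdrawal and missed syncing are unrelated to wear.

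**The case against.** The strongest reply is that section 3.1 promises only to explore trends, plans no test and feeds no aim, so replacing cohorts with a correlation is partly preference. That stands as to weight. A reader might infer that the team will choose cuts to suit the adherence results, or that the trial carries a 12% or 22% error rate. The documents support neither: they do not say that cuts will follow adherence, and those rates need a p-value that nobody plans to compute.

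Second, the gain assumes a roughly linear relation. If only the sickest patients adhere poorly, Spearman has no advantage over tertiles, and a well-placed cut does better. This stands, although that advantage requires knowing the cut beforehand, and the plan names none.

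Third, ending each patient's denominator at withdrawal could erase the effect being sought. Section 5.2.3 allows withdrawal for "disease progression, the occurrence of an adverse event or a concurrent illness", but the same sentence also lists noncompliance. Where withdrawal is itself non-adherence, the fixed-period correlations of 0.08 to 0.22 are signal and 0.00 is wrong. This stands, so neither denominator alone is adequate.

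**Conclusion.** The point holds as a cheap improvement to an exploratory analysis, not as an error in a main result. Section 3.1 leaves the severity variable, number of cohorts, cut-points and adherence measure open, and lets the cohorts be formed once adherence is known. Naming them in advance removes the doubt about independence.

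Using FEV1 without grouping adds a modest gain over pre-fixed tertiles (2 to 5 points) and a larger one over a median split (6 to 17 points), under bivariate normality and the assumed correlations. Under the assumed step it is about 6 to 7 points behind a correctly placed cut. At n = 21 the answer stays imprecise by any method. All of this takes lung function as the intended measure of severity, which is the natural but not the stated reading.

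**What to change.** In section 3.1:

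- Name the severity variable. If it is lung function, make the main exploratory analysis the Spearman correlation, with 95% CI and a scatter plot, between continuous baseline FEV1 (one scale named in advance) and one adherence measure: the proportion of days with use over 20 hours. If another measure is meant, name it in advance and treat it the same way.
- Keep any cohort table as descriptive, with cuts fixed from baseline FEV1 alone before adherence data are compared.
- Show the result with each patient's days in the study as denominator and again with the full planned follow-up period, and report withdrawals by baseline FEV1.
- Keep patients with incomplete downloads, as section 9.3 requires. That section does not say how to score their missing days, so show days without upload both as not met and as missing.

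The cost is a few sentences and no new data, visits or patients. The main result is no longer presented by clinical group, and FEV1 alone is narrower if severity means more than lung function.

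Two inconsistencies bear on the denominators but are separate points. The Protocol Summary gives a follow-up of 3 to 5 months, against "A patient may remain in the study up to 3-months" (5.2.1) and "Patients will be followed for 90 days after enrollment or until death, whichever occurs first" (6.2). Section 1 (Methods) provides spare devices for losses, whereas section 5.1.3 says that lost devices are not replaced. Each pair must be reconciled.
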